9.3 POPULATIONS FOR ANALYSES

All analyses will be performed on an intention-to-treat basis. If poor attendance at acupuncture treatments is observed, we will perform a per-protocol analysis as a sensitivity analysis.

9.4 STATISTICAL ANALYSES

9.4.1 GENERAL APPROACH

Discrete variables will be summarized using frequencies and percentages, while continuous variables will be summarized by means and standard deviations. If the continuous variables are found to be skewed, we will instead report medians and interquartile ranges. Statistical significance will be determined using p-values less than 0.05 and 95% confidence intervals, unless otherwise indicated. All inferential tests will be two-sided. For descriptive statistics (means, SDs, proportions) where no inferential statistics were conducted, we will refrain from making confirmative statements. All covariates will be pre-specified in the sections below. Any additional analyses will be described as post-hoc and exploratory.

Distribution of the outcome variables will be assessed prior to conduct of our analyses to determine if the planned tests are appropriate. If variables are found to be non-normally distributed we will explore the use of log-transformations or non-parametric tests such as the Wilcoxon-Rank Tests.

9.4.2 ANALYSIS OF THE PRIMARY ENDPOINT(S)

The number of headache days per 4 weeks will be captured via a headache diary. The primary outcome, change in number of headache days per 4 weeks between the pre-treatment assessment and 4-week post treatment assessment, will be compared using a two sample t-test. We will present the mean change by group with corresponding standard deviations. If baseline differences are found between study groups, they will be adjusted for using a linear regression model. In addition, a mixed-model analysis of variance (ANOVA) will be performed with data from all three time points. The outcome will be number of headache days per 4 weeks and it will be adjusted for group, time, and a group*time interaction. If significant interactions exist, line plots and post hoc tests will be used to define the nature of the interaction.

Prior to analysis, we will plot our outcomes to examine their distribution and decide whether we should consider non-parametric analyses. Only subjects with complete data from both pre-treatment assessment and 4-week post treatment assessment will be included in the final analysis. Data will be analyzed per an intent-to-treat approach regardless of actual treatment received. If a large proportion of missing data is noted, we will compare baseline characteristics of subjects who completed the treatment with those who were lost to follow-up.

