6.3 MEASURES TO MINIMIZE BIAS: RANDOMIZATION AND BLINDING

Randomization:

Randomization will be performed with a 1:1 allocation ratio. Balanced treatment assignments will be achieved using permuted block randomization with random block sizes stratified by gender. This decision was based on evidence that females in this population reported higher rates of headaches.³³ The study biostatistician will generate a randomization schedule using the SURVERYSELECT procedure in SAS. Assignments will not be seen by other study personnel in advance and will not be changed after randomization.

Blinding:

Study personnel will be unblinded to the randomization, as it will be clear the number of participants who receive 5 acupuncture treatments versus those that receive 10. In addition, it will be clear to participants which treatment group they are in and it will be impossible to blind them from this information.

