9.2 SAMPLE SIZE DETERMINATION

We require 18 subjects in each study group to achieve 80% power at a 5% significance level for our primary hypothesis (PASS software version 11). The primary analysis is a a two-sided two-sample t-test comparing the mean number of headache days over 4 weeks from a parallel-group design. We hypothesize that, while both groups will have decreased headaches, 10 treatments will greater alleviate headaches when compared to 5 treatments over a 5-week treatment period. For analysis purposes, we will analyze the data such that the opposite could be shown (5 treatments better reduces headaches). The null hypothesis is that there will be no difference between treatment groups. To conduct the power calculation, we assumed an equal standard deviation of 4.47, 33 equivalence limits of ± 1 SD, and a true difference between means of 0. No interim analyses are planned. The potential effect on our power if our estimates for the effect size are inaccurate are displayed in the table below.

N	δ	Σ	Power	Alpha
36	4	4.5	0.742	0.05
36	4.5	4.5	0.835	0.05
36	5	4.5	0.903	0.05

N = total sample size; δ = treatment effect (change); σ = standard deviation.

Based on preliminary estimates, we do not anticipate difficulty recruiting 40 subjects. HealthPartners Physical Medicine and Rehabilitation physicians see approximately 25 individuals with CPTH per month at the Neuroscience Center. Therefore we will need a 16% enrollment rate to reach our recruitment goal in the allotted time frame. In addition, we also plan to recruit and enroll from other HealthPartners clinics and within the community. If we see a 20% reduction in sample size due to dropout, withdrawal, or missing data, our power will be 75.8% to detect a similar effect size. This, and other possible changes in power due to attrition, are listed in the table below.

N	μ1	μ2	δ	σ	Power	Alpha
28	26	21.5	4.5	4.5	0.727	0.05

30	26	21.5	4.5	4.5	0.758	0.05
32	26	21.5	4.5	4.5	0.787	0.05
36	26	21.5	4.5	4.5	0.835	0.05

N = total sample size; μ 1 = mean of 5 treatment group; μ 2 = mean of 10 treatment group; δ = treatment effect (change); σ = standard deviation.

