9.4.5 BASELINE DESCRIPTIVE STATISTICS

Baseline variables will be compared between groups to ensure randomization achieved balanced treatment assignments. This will include demographics (e.g. gender, age, race) and medical history (e.g. length of stay in hospital after injury, discharge destination). All such variables are listed in section 8.1 of this document. Variables will be summarized using descriptive statistics (e.g. mean and SD, or frequency and proportion) and compared inferentially. Continuous variables will be compared using two-sample t-tests or Wilcoxon rank tests and discrete variables will be compared using chi-square tests for independence or Fisher's exact tests.

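### Section 9.4.2 adjusts the primary comparison only if undefined baseline differences are found; one fixed model with arm, baseline headache days and gender should lead

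*Combined protocol and SAP*

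**What the plan says.** Section 9.4.2 defines the primary outcome as change in headache days from the pre-treatment 4 weeks to the 4 weeks after treatment. It "will be compared using a two sample t-test". The next step is conditional: "If baseline differences are found between study groups, they will be adjusted for using a linear regression model". The section does not list covariates, define a difference as found, or rank the two results. The additional mixed model contains only group, time and their interaction.

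Other sections bear on this:

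- Section 9.2 calls a two-sided two-sample t-test the primary analysis, but on mean headache days, not change.
- Section 9.4.1 states: "All covariates will be pre-specified in the sections below". It also sets a general significance level of p<0.05.
- Section 9.4.5 states: "Baseline variables will be compared between groups to ensure randomization achieved balanced treatment assignments". It names the tests and refers to section 8.1 for the variables. Two of its own examples, hospital length of stay and discharge destination, are not in 8.1.
- Section 6.3 uses "permuted block randomization with random block sizes stratified by gender". Gender enters no primary model; section 9.4.7 only summarizes outcomes by it. The same section says: "Study personnel will be unblinded to the randomization".

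**The concern.** 9.4.1 promises pre-specified covariates, and 9.4.2 then leaves them to be found in the data. A trigger of p<0.05 and a pool of candidates can be pieced together from 9.4.1, 9.4.5 and 8.1, but 9.4.2 refers to none of them and the pool is inconsistent. Whether the regression takes over as the lead result or only supports the t-test is left to be decided after the data are in, by staff who know the allocation.

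Two things are at stake. One is type I error, if the more favourable result can be chosen. The other is precision: baseline headache days may be a strong predictor of the outcome, and a rule that uses it only after a chance imbalance discards most of its value.

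**Working it through.** **1. Inputs.** From 9.2: 18 per arm, difference 4.5 days, two-sided alpha 0.05, and "we assumed an equal standard deviation of 4.47" (shown as 4.5 in the tables). Not in the documents, so assumed: baseline-to-follow-up correlation r of 0.3, 0.5 or 0.7; the baseline SD; and whether 4.47 is the SD of a 4-week count or of change.

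**2. The plan's own figure.** Noncentrality = difference / (SD × √(2/n)) = 4.5 / (4.47 × √(2/18)) = 3.02 on 34 df, which gives power 83.5%. Differences of 4 and 5 give 74.2% and 90.3%. All three match 9.2. These figures are for an unadjusted t-test.

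**3. What each analysis does to the SD.** Let F be the follow-up SD and B the baseline SD.

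- Change score: SD = √(F² + B² − 2rFB), 34 df.
- ANCOVA with baseline and gender: residual SD = F√(1 − r²), 32 df.

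With F = B = 4.47 and r = 0.3:

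- Change: 4.47 × √1.4 = 5.29; noncentrality 4.5/(5.29/3) = 2.55; power 70%.
- ANCOVA: 4.47 × √0.91 = 4.26; noncentrality 4.5/(4.26/3) = 3.17; power about 86%.

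With B = 2.5 and r = 0.5:

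- Change: √(19.98 + 6.25 − 11.18) = 3.88.
- ANCOVA: 4.47 × √0.75 = 3.87. There is nothing to gain.

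The change score fixes the baseline slope at 1; ANCOVA estimates it, and its target is rF/B. In the second case that is 0.5 × 4.47/2.5 = 0.89, already close to 1.

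**4. Power by simulation** (100,000 trials per scenario, 6 women and 12 men per arm). The conditional rule here is ANCOVA if baseline headache days differ at p<0.05, otherwise the change t-test. Cells are change t-test / conditional rule / fixed ANCOVA, in %.

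| Scenario | r = 0.3 | r = 0.5 | r = 0.7 |
|---|---|---|---|
| Equal count SDs of 4.47 | 70/71/86 | 83/84/91 | 97/97/98 |
| 4.47 read as SD of change | 83/85/95 | 83/84/91 | 83/84/88 |
| Counts capped at 28 days | 82/83/89 | 91/91/92 | 97/97/97 |
| Baseline SD 2.5 | 84/84/86 | 92/92/92 | 98/98/98 |

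Before rounding, the conditional rule never gains more than 1.2 points. Fixed ANCOVA ranges from a loss of 0.7 (baseline SD 2.5, r = 0.5) to a gain of 15.8 (equal SDs, r = 0.3). Dropping gender changes ANCOVA power by at most 0.2 points if gender has no effect, and by 1.0 point with an assumed 3-day effect.

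**5. Type I error by simulation.**

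| Use of the two analyses | Type I error |
|---|---|
| Change t-test alone | 4.9-5.2% |
| Fixed ANCOVA | 4.9-5.2% |
| Trigger applied mechanically | 3.9-5.1% |
| Better p-value; regression only if baseline headache days differ at p<0.05 | about 5.0-5.4% |
| Better p-value; ten independent candidates tested at p<0.05 (assumed number) | 5.6-6.4% |
| Better p-value; both run in every trial | about 6-8% |

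With ten candidates, chance alone triggers adjustment in 1 − 0.95¹⁰ = 40% of trials. The regression then often carries covariates unrelated to the outcome. With a difference of one SD and equal SDs, power of that rule at r = 0.3, 0.5 and 0.7 is 66.8%, 81.2% and 94.9%, slightly below the change t-test (69.1%, 83.1%, 96.5%) and below fixed ANCOVA (85.5%, 92.2%, 97.7%).

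**The case against.** The best defence is that the plan is less open than it looks. Sections 9.2 and 9.4.2 both name a t-test, 9.4.1 calls any additional analysis post hoc and exploratory, and 9.4.1 with 9.4.5 supplies a significance level and named tests. A reader might infer from 9.4.2 that nothing is fixed; the documents do not support that. What remains is a gap in linkage and ranking: 9.2 and 9.4.2 put the t-test on different forms of the outcome, and 9.4.2 says that differences will be adjusted for without saying which result then leads.

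A reader might also infer a type I error of 6-8% under this plan. That needs both analyses in every trial and a free choice between them. The text runs the regression only after a difference is found, so the excess is smaller, and it is absent if the rule is followed mechanically.

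Nor is a 16-point gain to be expected. Section 9.2 assumes a mean of 26 days on a 28-day scale. With counts that close to the ceiling, ANCOVA gains 6.6, 1.7 and -0.3 points at r = 0.3, 0.5 and 0.7. This part of the defence stands: the case for a fixed model rests first on pre-specification, with power as a possible benefit.

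Finally, the baseline value might be thought compromised, because the schedule in 1.3 puts randomization at the Pre-treatment Visit, before the first 4-week diary. But 4.1 requires only that randomization precede the first treatment, and no section says when participants learn their arm. Bias cannot be inferred from this. It would affect the change score equally.

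**Conclusion.** The point holds in a limited form and should be acted on. The planned t-test is valid. The defect is a conditional adjustment with no covariate list and no ranking, which conflicts with 9.4.1 and omits the stratification factor. The inflation of type I error from choosing between results is small under the rule as written. The larger cost is a rule that recovers at most about 1 point of power where a fixed model could recover up to about 16, and puts at most about 1 point at risk. These figures assume 18 per arm, a difference of 4.5 days, and correlations and baseline SDs that the documents do not give. The gain is near zero if the baseline SD is small, or if counts sit near the 28-day ceiling with correlation 0.5 or more. Gender belongs in the model because allocation was stratified on it, not for power.

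Section 9.2 also mixes equivalence inputs, including equivalence limits "and a true difference between means of 0", with a superiority test. That is a separate matter and adds no weight here.

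**What to change.** In 9.4.2:

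- Make the primary analysis a linear model of headache days in the 4 weeks after treatment on arm, baseline 4-week headache days and gender, fitted whatever the baseline comparisons show.
- Name the adjusted difference with its 95% CI as the lead result.
- Delete the conditional-adjustment sentence.
- Keep the change-score t-test, and any log-transformed or rank-based analysis, as labelled sensitivity analyses. Sections 9.4.1 and 9.4.2 currently let outcome plots decide among these, and that should no longer change the lead result.

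In 9.2, name the same analysis and say whether 4.47 is the SD of a count or of change. With baseline in the model, follow-up count and change give the same arm effect, so the mismatch between 9.2 and 9.4.2 disappears.

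State whether allocation is disclosed before the baseline diary is complete; if it is, report that as a limitation of the baseline value.

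Cost: no new data or participants, two degrees of freedom (32 instead of 34), and at most about 1 point of power. The amendment history in 10.4 shows treatment under way by May 2021 and staff are unblinded, so the change needs a dated amendment recording that it was made without sight of outcomes by arm.

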7.1 DISCONTINUATION OF STUDY INTERVENTION/EXPERIMENTAL MANIPULATION

When a participant who signed the consent form chooses to discontinue participation in the study or study intervention, or if the principal investigator and co-investigators determine that a participant should discontinue participation, they will be withdrawn from the study. A withdrawal will either be defined as 'Patient Withdrawal' or 'Principal Investigator Withdrawal'. The participant will be asked to complete an early withdrawal phone call 7-14 days from the date the intervention was discontinued. The purpose of the phone call will be to record any AEs or serious adverse events (SAEs) that may have occurred after the discontinuation of treatment. Research staff will attempt to call the participant up to 3 times.

The data that will be collected at the time of study withdrawal will include the following:

The reason(s) for discontinuation of the study intervention

The data that will be collected during the early withdrawal phone call will include the following:

AEs or SAEs that occurred since the time of withdrawal

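### The primary analysis is called intention-to-treat but is complete-case by assigned arm, and people who formally stop acupuncture have no planned route to the primary endpoint

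*Combined protocol and SAP*

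**What the plan says.** **Analysis set.** Section 9.3 states "All analyses will be performed on an intention-to-treat basis". It adds "If poor attendance at acupuncture treatments is observed, we will perform a per-protocol analysis as a sensitivity analysis". Section 9.4.2 repeats the principle: "Data will be analyzed per an intent-to-treat approach regardless of actual treatment received". The same section restricts who is analysed: "Only subjects with complete data from both pre-treatment assessment and 4-week post treatment assessment will be included in the final analysis".

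**Primary test.** Section 9.4.2 compares change in headache days per 4 weeks, from pre-treatment to 4 weeks post-treatment, by two-sample t-test. Section 9.4.1 allows a fallback if the data are not normal: "we will explore the use of log-transformations or non-parametric tests such as the Wilcoxon-Rank Tests". A further model follows: "In addition, a mixed-model analysis of variance (ANOVA) will be performed with data from all three time points".

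**Missing data.** The one planned step is conditional: "If a large proportion of missing data is noted, we will compare baseline characteristics of subjects who completed the treatment" with those lost to follow-up. No imputation, missing-data assumption or missing-data sensitivity analysis is given.

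**Stopping.** Section 7.1 covers a consented participant who "chooses to discontinue participation in the study or study intervention", or whom the investigators decide should discontinue. That person is withdrawn from the study. The data listed are the reason for stopping and, in one call 7 to 14 days later, any AEs or SAEs. Section 8.3.9 uses the same withdrawal and safety call for pregnancy during treatment.

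**Diary.** Under 1.3, instructions and the paper form for the post-treatment diary are given only at the last acupuncture visit. The diary itself is a weekly e-mailed survey (8.1).

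**The concern.** Analysis by assigned arm is one part of intention-to-treat. The other is keeping everyone who was randomised, and the complete-data rule gives that up. The dose comparison is then made in a subset formed after randomisation.

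The withdrawal procedure makes part of that loss certain. Someone who finds the visits too much, but would still answer a weekly e-mail, is not asked for headache data once withdrawn. The trial is unblinded and compares 5 visits with 10, so unequal stopping is plausible, though nothing in the documents shows it. Section 9.2 treats a 20% loss only as reduced power and does not consider bias. A reader who trusts the intention-to-treat label would believe the comparison is protected by randomisation when it is not fully so.

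**Working it through.** **1. The plan's own figures.** Inputs from 9.2: two-sided two-sample t-test, alpha 0.05, SD 4.47 (shown as 4.5 in the tables), difference 4.5 days (26 vs 21.5). Noncentral-t power with SD 4.47 is 0.835 at N = 36, 0.787 at N = 32, 0.7585 at N = 30 and 0.727 at N = 28. The tables give 0.835, 0.787, 0.758 and 0.727, so they reproduce. They vary only N and therefore say nothing about bias from who is missing.

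**2. Who reaches the endpoint.**

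| Randomised participant | Post-treatment diary planned? | In the t-test? |
|---|---|---|
| Attends all sessions, completes both diaries | Yes | Yes |
| Misses sessions, not withdrawn | Yes, if a last visit takes place | Yes, if both diaries are complete |
| Stops the intervention, or is withdrawn by the investigators | None listed in 7.1 | No, if this happens before the post-treatment diary |
| Never starts | None described | No |

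**3. Illustrative bias.** The documents give no loss by arm and no outcomes for people who stop, so the following are assumptions:
- no true difference between arms;
- SD of change 4.47;
- 20 randomised per arm (enrolment 40, 1:1);
- 20% total loss, as considered in 9.2;
- correlation r between the tendency to be lost and poor response of 0.3 to 0.5.

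With loss fractions a and b in the two arms, z_a and z_b the matching normal quantiles, and φ the normal density:

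bias = 4.47 × r × [φ(z_a)/(1 − a) − φ(z_b)/(1 − b)]

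For 30% vs 10% the bracket is 0.4967 − 0.1950 = 0.3017. For 25% vs 15% it is 0.4237 − 0.2743 = 0.1494.

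| Loss | Bias, r = 0.3 | Bias, r = 0.5 | Simulated type I error (r = 0.3, 0.5) |
|---|---|---|---|
| 30% vs 10% | 0.405 days | 0.674 days | 5.7%, 7.3% |
| 25% vs 15% | 0.200 days | 0.334 days | 5.4%, 5.6% |
| 20% vs 20% | 0 | 0 | 4.9%, 5.1% |

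Type I error is from 30,000 simulated trials per row. The bias favours the arm with more loss when poor responders leave, and reverses when good responders leave.

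**4. A cruder version.** If people who stop improve g days less than completers in both arms, the bias is (difference in loss) × g. With 20 points and g = 4.5 days this is 0.20 × 4.5 = 0.9 days, with rejection about 8.4% for 18 vs 14 analysed. This is a somewhat stronger link than r = 0.5. The largest gap possible under a normal response with SD 4.47 is 4.47 × φ(z)/[f(1 − f)], where f is the loss fraction: 7.4 days at 30% loss and 8.7 at 10%. So g = 4.5 corresponds to r of about 0.61 (4.5/7.4) and 0.52 (4.5/8.7).

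**5. What the mixed model could recover.** Maximum likelihood on all randomised, 30% vs 10% loss, r = 0.5, SD of change held at 4.47. Values are for baseline to follow-up correlations of 0.3 / 0.5 / 0.7; signs are dropped, as the two mechanisms act in opposite directions.

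| Loss depends on | Complete-case bias (days) | Mixed-model bias (days) |
|---|---|---|
| Baseline headache days | 0.40 / 0.34 / 0.26 | 0 |
| Response (change) | 0.67 / 0.67 / 0.67 | 0.47 / 0.53 / 0.59 |

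With days limited to 0 to 28, baseline mean near 26 and loss depending on response, the model moves the bias only from 0.37–0.41 to 0.34–0.39 (r = 0.3) and from 0.62–0.64 to 0.59–0.62 (r = 0.5).

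**The case against.** **The label is terminology.** Section 9.4.2 states its inclusion rule openly, beside its own meaning of intent-to-treat. A careful reader can see who is analysed. That stands as mitigation, but the 9.3 statement is unqualified, and relabelling does not recover the missing diaries.

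**The mixed model handles it.** It can use partial data, but it is additional to the t-test, and 9.4.2 does not say whether the complete-data rule covers it. Someone withdrawn during treatment would supply only baseline data. A reader might infer that the mixed model ought to become the primary analysis. The case is not strong: it would be a late change in an unblinded trial, for an outcome near its ceiling, with little gain when loss depends on response.

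**Poor attenders are kept.** This is right. Investigator discontinuation under 7.2 is discretionary, and per-protocol analysis is only a sensitivity analysis. It would be wrong to read the plan as dropping everyone who misses sessions.

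**Three further inferences go beyond the text.**
- Section 10.4 raises enrolment to 40 because of withdrawals. This does not establish loss after randomisation: 7.1 applies withdrawal to anyone who consented, and 5.5 expects 50 consents for 40 randomised.
- Section 7.2 lets randomised people who never start be replaced. This does not remove them from the analysis set: 9.3 and 9.4.2 imply they stay, and missing diaries are what would exclude them.
- The 1.3 table places randomisation at Visit 1, which would make an incomplete baseline diary a post-randomisation exclusion. But 4.1 says only that it precedes the first treatment visit, and the order shown in 1.2 fits either reading.

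**The bias is small.** Against 4.5 days it is modest unless loss is very uneven. That stands.

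**Conclusion.** The point holds. The primary analysis as written is complete-case by assigned arm, and 7.1 leaves people who formally stop acupuncture without a planned route to the endpoint. Both follow from the text and need no assumption.

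The consequence is conditional. Bias arises if loss differs between arms, or the outcome gap between those lost and those kept does, and loss is related to response. The documents give neither rates nor outcomes, so neither size nor direction can be derived. At 30% vs 10% loss and r of 0.3 to 0.5 the bias is about 0.4 to 0.7 days, with type I error about 6 to 7%; the cruder version in step 4 reaches 0.9 days. At 25% vs 15% it is 0.2 to 0.3 days with type I error about 5.5%. Equal loss with an equal gap gives none. The documents do not support saying that the trial's result is biased. This should be fixed, but it does not by itself invalidate the design.

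**What to change.** 1. **Section 7.1, data collection only.** Separate stopping acupuncture from leaving the study. Keep sending the existing weekly e-mail diary to randomised participants who stop or never start, unless they withdraw consent to data collection. Count their 4-week window from a stated anchor, such as the planned date of the last session. This matters most, because no analysis can replace outcomes that were not collected.
2. **Section 9.4.2, before outcome data are analysed.** State that the complete-data restriction does not apply to the mixed model, which uses all randomised participants with any diary data and is reported beside the t-test. Then either lift the restriction for the primary analysis, saying how missing values are handled, or relabel the t-test as a complete-case analysis by assigned arm.

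**Optional.** Make the mixed-model contrast in change from pre-treatment to 4 weeks the primary estimate, with the t-test or its non-parametric fallback as sensitivity. For participants not yet enrolled, randomise after the baseline diary and before Visit 2. As a clarification, state that replaced randomised participants stay in the intention-to-treat set and are reported.

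**Cost.** A dated, disclosed amendment and a few more diary e-mails, with no new instrument. Item 1 helps only participants not yet past that step. Randomising later would also mean later booking of treatment visits.
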